5. STUDY OBJECTIVES OR HYPOTHESES

5.1 Hypothesis

We hypothesize that idebenone, through its combined effect on facilitation of mitochondrial metabolism and limitation of oxygen radical-induced CNS damage, will inhibit CNS tissue destruction in PP-MS patients.

5.2 Goals of the study

The primary goals are:

1. To determine the safety of long-term (24 months) idebenone therapy at 2250 mg/day in patients with PP-MS.
2. To determine the efficacy of idebenone versus placebo in inhibiting individualized rates of CNS tissue destruction as measured by clinical biomarkers and quantitative imaging biomarker of brain atrophy (i.e. ventricular volume)

The secondary goals are:

1. To investigate the mechanism of action of idebenone in PP-MS.
2. To determine/define biomarkers of mitochondrial dysfunction and oxidative damage in PP-MS patients.
3. To define biomarkers indicative of therapeutic effect of idebenone on mitochondrial dysfunction and on limiting oxidative damage in PP-MS patients.
4. To collect longitudinal data in the placebo arm that will allow us to evaluate whether the assumptions on which we based our primary analysis (i.e. that the CNS tissue destruction is intra-individually linear, but inter-individually different within 3 year time period) are

correct or not. This will allow us to calculate more precise sample size/power calculations for future neuroprotective trials in PP-MS.

6. SUBJECTS

6.1 Study population

The study population will consist of 66 patients (33 per arm) with clinically definite PP-MS; age 18-65 (inclusive) with disability ranging from none to moderately severe (EDSS 1-7, inclusive). We will exclude children, because a diagnosis of PP-MS is virtually nonexistent in children, and we will limit the age of the participants up to 65, because of evidence that remyelination and repair strategies may be ineffective in older patients (*Crutcher 2002, Confavreux and Vukusic 2006*).

Interested patients (i.e. those who respond to the advertisement or are referred by an outside physician) will be interviewed over the phone by one of the investigators and will be asked to fill out the standard NIB questionnaire (Appendix G, page 71) utilized also by the NIB natural history protocols 09-N-0032, and 89-N-0045. Patients will be informed that the information collected in the questionnaire is necessary for us to determine their eligibility to enter the protocol and that collection and review of these personal data will be performed under NIH/NINDS principles for patient confidentiality. Verbal consent for collection and review of the personal data will be obtained from interested patients by study investigators. The following standard language for obtaining verbal phone consent will be used:

“Thank you for calling the Neuroimmunology Branch. I am (name). The Neuroimmunology Branch studies multiple sclerosis, along with other diseases of the central nervous system. If you are interested in participating in one of our studies, I will send you our screening questionnaire. This questionnaire will expedite the screening process to see if you qualify for any of our current or future studies. The questionnaire takes about 10 minutes to complete. If you appear to be eligible for a study, you will be invited to come to the NIH for a clinical visit and possible enrollment in one of our studies.

The questionnaire asks you to provide confidential information related to your health. You must understand the risks and possible benefits of completing this questionnaire and then you can decide whether to continue.

First, the benefits. There is no direct medical benefit to you from completing this questionnaire, but we should be able to determine whether it is worth your time to come in for a clinical visit and possible enrollment in a study.

6.3 Exclusion criteria

1. Alternative diagnoses that can explain neurological disability and MRI findings
2. Clinically significant medical disorders that, in the judgment of the investigators could cause CNS tissue damage or limit its repair, or might expose the patient to undue risk of harm or prevent the patient from completing the study
3. History of hypersensitivity reaction to idebenone or coenzyme-Q₁₀
4. Pregnant or lactating women. All women of child-bearing potential must have a negative pregnancy test prior to the medication phase of the study.
5. Abnormal screening/baseline blood tests exceeding any of the limits defined below:

- i. Serum alanine transaminase or aspartate transaminase levels greater than 3 times the upper limit of normal values
 - ii. Total white blood cell count $< 3,000/\text{mm}^3$
 - iii. Platelet count $< 85,000/\text{mm}^3$
 - iv. Serum creatinine level $> 2.0 \text{ mg/dl}$ or eGFR (glomerular filtration rate) < 30
 - v. Positive pregnancy test
6. Patients who are receiving any immunosuppressive therapies (including cytostatic agents) due to the concern that these drugs may contribute to neurodegeneration or limit CNS repair

7. STUDY DESIGN AND METHODS

7.1 Study overview

This is a Phase I/II, double-blind, placebo controlled, baseline versus treatment with 2 parallel study groups (Figure 1) and an adaptive trial design.

Based on current sample size estimates we expect to screen up to 85 PP-MS to yield at least 66 patients that will finish the treatment phase of the study. These patients will be randomized 1:1 to receive either active therapy (idebenone 750mg po tid) or matched placebo. The treatment phase of the trial will be preceded by a 1 year pre-treatment baseline period, which will serve a dual purpose: 1. To collect individualized data on biomarkers of CNS tissue damage and 2. To use these longitudinal data for the selection of the primary outcome measure and for more precise sample size estimates.

7.2 Recruitment

This protocol will be advertised on the NIH website and through patient support groups such as the National MS Society (NMSS). Active recruitment will include a letter to neurologists in the greater Washington DC area and to MS specialists in the states of Virginia, West Virginia, Maryland, Delaware, New Jersey and Pennsylvania. We have contracted the recruitment services of the North American Research Committee on Multiple Sclerosis (NARCOMS). The NARCOMS registry is a database of MS patient volunteers who are interested in participating in research. NARCOMS collects volunteer data, and then will match the volunteers to applicable studies. Volunteers are then mailed information about the studies they match, and the participant is able to contact the studies they are interested in. Finally, eligible patients will also be recruited from NIB natural history protocols (09-N-0032 and 89-N-0045). Because this natural history protocol collects identical clinical, MRI and paraclinical data as the present protocol, we will use data already collected under the natural history protocol in order to fulfill the requirements of the pre-treatment baseline. This will allow eligible PP-MS patients to proceed to the randomization and treatment phase of the current protocol without unnecessary delay.

Patient advertisement (for NIH website and for NMSS bulletin) and the letter to the neurologists are provided in Appendix F.

7.3 Screening methods

Patients who contact the study either through physician or self referral will be screened initially by phone. Interested patients may be requested to complete the NIB MS questionnaire (Appendix G) and to provide pertinent medical records (including MRI of the brain/spinal cord). The blank questionnaire may be sent to the potential patient by mail, fax, or email. The completed questionnaire and medical records are then mailed or faxed to the protocol research contact. Upon receipt of the records and imaging studies, the patient will be contacted to confirm the receipt of the requested information and, provided that review of the documentation does not identify any exclusion criteria, the patient will be invited to participate in the study. Interested patients will be scheduled for outpatient admission to the Clinical Center.

Subjects who sign the informed consent but are excluded later based on abnormal laboratory findings will be defined as screen failures and counted toward patient accrual. When 30 subjects complete the pre-treatment baseline, we will perform an interim analysis for more precise sample size calculations (See Sample size calculation, section 11) and for selection of the most sensitive primary outcome measure. This analysis will not require unblinding, and will not affect final statistical analysis. Instead, it will help us to perform more precise power calculations based on longitudinal data collected utilizing neuroimaging biomarkers specific for this trial. We expect that this interim analysis will allow us to increase the power and/or decrease the sample size, based on assumptions specified under Section 11 and outlined in Figure 2.

To allow for approximately 20% screening failures, the accrual ceiling (based on current estimates of sample size) will be set at 80 patients.

7.4 Study design

All eligible patients will undergo combined neurological, neuroimaging and research biomarker/immunological evaluations as outlined in Fig. 1 for the baseline period. The complete baseline evaluation will require approximately 4 outpatient visits in approximately 1 year. Each outpatient visit will last 3-5 hours.

Patients who complete the baseline period will be randomized to active treatment or placebo by block stratification (by block size of 2) using a single condition: 1. Age (age <50 and age ≥50). Because epidemiological data indicate that age is a major determinant of the efficiency of CNS repair (*Crutcher 2002, Confavreux and Vukusic 2006*), this randomization strategy will ensure that both placebo and active treatment groups are comparable in this respect. The majority of patients are diagnosed with PP-MS around age 40. Furthermore, using block size of 2 will assure balanced distribution of the first 30 patients into placebo and active treatment groups (i.e. 15 patients per group). Randomization will be performed by the NIH pharmacy. The NIH pharmacy will maintain the study code key and release it to the investigators only after completion of the trial and finalization of the database. The NIH pharmacy may release the study code to the DSMB, if requested.

After randomization, patients will be followed by combined neurological, neuroimaging and research biomarker/immunological evaluations as outlined in Fig. 1 for an additional 24 months.

The time commitment will include at least 6 outpatient visits in the 2 year period. Each outpatient visit will last 2-5 hours.

According to the negotiated CTA, Santhera Inc. will supply a sufficient amount of idebenone for completion of the proposed trial (i.e. 2 year dosing for 40 patients). There is no negotiated provision for Santhera to continue to provide drug on a compassionate basis for any of the patients after completion of the trial.

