4.7 Rationale for current study design

The clinical experience with use of antioxidants in MS is very limited: although a few trials of antioxidants in MS have been reported (*Jensen and Clausen 1986, Spitsin, Hooper et al. 2001, Yadav, Marracci et al. 2005*), all have been small studies of short duration and offered only very limited insight on clinical efficacy (*Spitsin, Hooper et al. 2001*).

Based on this background information, we propose to use idebenone in a proof-of-principle placebo-controlled cross-over Phase I/II clinical trial for PP-MS (Figure 1). Because there are no other therapeutic options for PP-MS, a placebo arm is both ethically justifiable and important to ensure an unbiased evaluation of MRI, clinical and immunological outcome measures. 1:1 randomization between active treatment and placebo will optimize statistical power for detecting differences in the outcome measures.

4.7.1 Figure 1

Idebenone in PP-MS clinical trial design

[figure not shown]

Figure 1: At least one year of pre-treatment baseline will be followed by 1:1 randomization to placebo and idebenone

750mg tid for 2 years. All outcome measures will be collected every 6-12 months as indicated.

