Idebenone has not been administered (to our knowledge) to patients with presumed immune-mediated disorders and therefore the effect of idebenone on dysregulated immune responses in humans is currently unknown and difficult to predict. Because several functions of the immune system are dependent of the formation of ROS, a potent antioxidant may theoretically inhibit these functions. Among these are oxidative burst used by granulocytes and monocytes/macrophages to kill intracellular pathogens and granzyme A-, B- and K-mediated killing utilized by natural killer (NK) cells and some T cells. Granzyme-B mediated killing is only partially dependent on the formation of ROS, as it predominantly relies on activation of caspases. Because some of these immune functions (oxidative burst of monocytes/macrophages, including microglia and granzyme-B-mediated killing by cytotoxic T cells) are thought to contribute to CNS tissue damage in MS, theoretical inhibition of these functions by idebenone may have an overall beneficial effect in PP-MS patients.

Inhibition of oxidative burst utilized by granulocytes and monocytes/macrophages can theoretically lead to increased rates of infections; however, this was not observed in double-blinded placebo controlled randomized trials, including those that targeted elderly and disabled patients (e.g. AD), which are known to be more susceptible to infectious complications. Therefore, idebenone is considered to be a safe and well tolerated agent.

Idebenone at high doses (60-75 mg/kg/day or about 3600-4500 mg/day) may cause orange discoloration of urine in few patients. It is unclear if this will occur at the dose of 2250mg/day. The orange discoloration of urine is completely harmless and urine will be monitored every 6 months by urinalysis in order to ensure that hematuria or hemoglobinuria is not mistaken for the orange discoloration due to idebenone.

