9.1.16 Monitoring of adverse events

The patient will be instructed to contact the investigator immediately should the patient manifest any sign or symptom perceived as serious during the period extending from performance of the first study procedure (e.g. drawing of a blood sample) up to and including 1 month after the last dose (telephone interview at month 25). After this period of time, the patient should report to the investigator only adverse events that are serious and perceived as possibly related to their participation in this study.

Additionally, the patient will be instructed to contact the investigator immediately if he/she believes that he/she has fathered/conceived a child. Testing would be performed to verify that the subject or subject's partner was pregnant. If the pregnancy test were positive, the patient would be instructed to immediately stop taking the study drug and his/her treatment assignment would be revealed to the investigators and the DSMB. The patient or partner would be counseled and followed closely during the pregnancy by the NIH research team and would implement any recommendations made by the DSMB.

Patients will be physically examined by the investigator approximately every 6 months for the study duration. Extensive laboratory monitoring of the following will occur every 6 months for the study duration: CBC with differential, Chemistry panel 20, and urinalysis and pregnancy test (for females with childbearing potential). Additionally, laboratory monitoring (CBC, chemistry panel with liver function tests) will be performed every 3 months after initiation of dosing of idebenone for the first year of treatment and every 6 months thereafter.

All adverse events occurring within 1 month following the last administration of the study medication must be recorded on the Adverse Event Form irrespective of severity and seriousness, and whether or not they are considered related to the study medication. Additionally, all serious adverse events (SAE) brought to the attention of the investigator during the period starting from the day of performance of the first study procedure to the telephone interview on month 25, must be recorded and reported to the FDA in accordance with federal regulations and NIH procedures. Any SAE reported by the patient after month 24, will be subjected to expedited reporting only if judged to be related to the study treatment by the Investigator.

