23.5 Modified McDonald's Diagnostic Criteria for PP-MS

(Polman, Reingold et al. 2005)

- 1) One year of disease progression (retrospectively or prospectively determined)
- 2) *Plus* two of the following:
 - a. Positive brain MRI (≥ 9 T2 lesions or ≥ 4 T2 lesions with positive VEP)
 - b. Positive spinal cord MRI (≥ 2 focal T2 lesions)
 - c. Positive CSF (isoelectric focusing evidence of oligoclonal IgG bands or increased IgG index, or both)

As with RR-MS, the alternative diagnoses that could explain insidious progression of neurological disability or MRI/CSF findings need to be searched for and ruled out before the diagnosis of MS can be concluded.

Do you have Primary Progressive Multiple Sclerosis?

If so, you may qualify for an NIH research study.

The Neuroimmunology Branch (NIB) of the National Institutes of Health is conducting a study to investigate the efficacy of an oral experimental drug in primary progressive multiple sclerosis. The study will be conducted at the NIH Clinical Center in Bethesda, Maryland, on an outpatient basis.

We are seeking participants:

- ages between 18-65
- diagnosis of Primary Progressive Multiple Sclerosis
- not taking any immunomodulatory drugs

The study involves a one year baseline after which participants will receive the medication or placebo for 2 years. Medical evaluations, MRIs, and blood work will be performed at scheduled intervals during the 3-year study. The visits will last 2-5 hours each and will be every month the first 3 months and then every 6 months for the remainder of the study.

There is no cost for participation.

Travel reimbursement will be provided.

Please call [contact] for more information about participating in this study. Please refer to study number 09-N-0197. [www. ClinicalTrials.gov](http://www.ClinicalTrials.gov)

Do you have Primary Progressive Multiple Sclerosis?

Researchers at the NIB are seeking adults ages 18-65 with a diagnosis of Primary Progressive Multiple Sclerosis to participate in a randomized, placebo controlled, double blind study investigating the efficacy of Idebenone in this disease. Participation will include medical evaluations, MRI, bloodwork, and lumbar puncture performed at the NIH Clinical Center on an outpatient basis.

Q. What's involved in the study?

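### Fixed blocks of 2, printed in the protocol of a single-centre trial, let one known allocation fix its block partner's allocation

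*Protocol*

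**What the plan says.** Protocol 7.4 randomises patients who finish the baseline year "by block stratification (by block size of 2"), "using a single condition: 1. Age (age <50 and age ≥50"). Protocol 4.7 gives the ratio: "1:1 randomization between active treatment and placebo will optimize statistical power". The reason offered for the block size is that "using block size of 2 will assure balanced distribution of the first 30 patients into placebo and active treatment groups (i.e. 15 patients per group"). The planned size is in Protocol 6.1: "The study population will consist of 66 patients (33 per arm"). There is one site; the recruitment advertisement that follows Protocol 23.5 states: "The study will be conducted at the NIH Clinical Center in Bethesda, Maryland, on an outpatient basis". SAP section 5 describes the design but not the randomisation.

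On protection of the code, Protocol 7.4 has the NIH pharmacy randomise and hold the key, releasing it to investigators only at the end and to the DSMB on request. Protocol 9.1.16 adds an exception during the trial. After a confirmed pregnancy in a participant or a participant's partner, "his/her treatment assignment would be revealed to the investigators and the DSMB". The section on criteria for stopping the study lets the DSMB ask for the allocation of a patient with a serious adverse event. Protocol 7.6.11 assesses blinding at month 6 and at the end, and bars the principal investigator from acting as clinical evaluator.

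**The concern.** Small fixed blocks are safe only while no allocation in the block becomes known. With blocks of 2 there is no slack: one known member determines the other. Staff at a single centre can see each patient's age and Month 0 date, so they can reconstruct the order within a stratum. The protocol tells them the block size.

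Two kinds of bias could follow.

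- **Assessment.** EDSS and Scripps NRS are scored by an examiner and both enter CombiWISE, the primary endpoint (SAP 4.2). A rater who knows a patient's arm could shift these scores without intending to.
- **Selection.** If the first of a pair is unblinded before the second is randomised, the coming assignment is known. Eligibility is rechecked at Month 0 (Protocol 25.1), one exclusion criterion rests on investigator judgement (Protocol 6.3), and visits may move by 4 weeks either way (Protocol 7.5.1). There is room for that knowledge to influence who is randomised next, and when.

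**Working it through.** **Inputs.** Block size 2, two age strata and the 15:15 target come from Protocol 7.4; the 1:1 ratio from 4.7; 66 patients from 6.1; the CombiWISE weights and AUC scaling from SAP 4.2.

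**1. The plan's own figure.** Fifteen complete blocks of 2 give 15 × 1 = 15 per arm, so 15:15 is reproduced if every block is complete. With two strata it is not strictly assured. Since 30 is even, the two stratum counts are both even or both odd. If both are odd, each stratum leaves one unpaired patient, and these two fall in the same arm with probability 1/2, giving 16:14. If 30–50% of patients are in one stratum (an assumption), the chance that both counts are odd is about 0.50. So P(16:14 either way) ≈ 0.50 × 0.5 = 0.25 and P(15:15) ≈ 0.75.

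**2. What one known allocation reveals.** In a 1:1 block of size b, suppose one patient's arm is known and that patient is not last in the block. The next patient has the opposite arm with probability (b/2)/(b − 1).

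- b = 2: 1/1 = 1.00
- b = 4: 2/3 = 0.667
- b = 6: 3/5 = 0.60

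If the known patient is last in the block, the next patient opens a new block and the probability is 0.50. With b = 2 the previous patient is then revealed instead. Averaged over positions, the chance of naming the next patient correctly is:

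- b = 2: (1 + 0.5)/2 = 0.75
- b = 4: (3 × 0.667 + 0.5)/4 = 0.625
- b = 6: (5 × 0.60 + 0.5)/6 = 0.583

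**3. Share of allocations fixed by earlier ones.** For block size 2m, the expected number determined by earlier members is 2m/(m + 1), a share of 1/(m + 1): 50%, 33% and 25% for sizes 2, 4 and 6. With 66 patients in 66/2 = 33 pairs, that is 33 patients. These shares apply only if all earlier allocations in the block are known.

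**4. Varying blocks.** If the first patient of a block is known and the size is undisclosed, with sizes equally likely, the next patient is opposite with probability (0.667 + 0.60)/2 = 0.633 for sizes 4 and 6. For sizes 2, 4 and 6 it is (1 + 0.667 + 0.60)/3 = 0.756.

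**5. What a rating shift would do.** A half-point on EDSS moves CombiWISE by 0.5 × 3.803 = 1.9 points. Ten points on Scripps NRS move it by 10 × 0.407 = 4.1. These are sensitivities, not estimates of bias.

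**6. Noise from shortened follow-up.** The SAP scales the treatment-phase AUC of changes from Month 0 by the square of its duration. Assume nominal visit times and independent errors of equal SD σ at each visit, including Month 0.

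- 24 months: weights 0.125, 0.125, 0.125, 0.0625 and −0.4375 on Month 0. Error SD = √(3 × 0.125² + 0.0625² + 0.4375²) σ = 0.49σ.
- 12 months: √(0.5² + 0.25² + 0.75²) σ = 0.94σ.
- 6 months: √(1² + 1²) σ = 1.41σ.

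**The case against.** The strongest reply is that no allocation is routinely visible. Treatment is double-blind with matching placebo, and the pharmacy holds the code. Blinding is formally assessed, and the principal investigator, who alone sees all data together, does not rate patients. An allocation revealed to investigators is not necessarily revealed to the rater. This reply stands as a limit on the size of the problem. It does not remove the mechanism, because section 9.1.16 puts an individual allocation in investigators' hands during the trial, and nothing planned traces block partners.

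The routes are also fewer than a reader might infer. The stopping section does not say that a DSMB request passes the allocation to investigators or raters. Urine colour is weak: Protocol 8.1 says idebenone at 60–75 mg/kg/day (about 3600–4500 mg/day) "may cause orange discoloration of urine in few patients", and leaves open whether this happens at 2250 mg/day. A guess from such a sign gives only an equally uncertain guess about the partner. Pregnancy should be uncommon, since contraception is required.

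The protocol does give a reason for its block size, balance in the first 30 patients. That reason carries little weight. The analysis of those patients uses pre-randomisation data and needs no unblinding (Protocol 7.3 and 11.5), so it does not depend on arm balance. Step 1 also shows that exact balance is not guaranteed.

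Finally, recruitment is complete (Protocol 11.6), and Protocol 7.6.10 reports that the analysis is finished with no significant efficacy. A new randomisation list can therefore help only a later trial.

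**Conclusion.** The weakness is real, and its remedy is a cheap improvement. A fixed, disclosed block of 2 means that each allocation learned by someone who also knows the randomisation order in the stratum reveals the block partner's allocation with probability 1.00. The corresponding chance for the next patient in a fixed block of 4 or 6 is 0.67 or 0.60. An unpaired last patient in a stratum exposes no one.

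Three stronger readings are not supported.

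- Learning any one allocation does not always reveal the next patient; that holds only when the known patient is first of the pair.
- Half of the allocations were not predictable in practice; the 50% share assumes earlier allocations are known.
- The primary endpoint is not shown to be biased. The documents report no count of unblindings and do not show that any reached a rater, so the effect on CombiWISE cannot be quantified.

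**What to change.** **For a trial using this template.** Draw block sizes at random within each age stratum and record them only in a pharmacy-held document. Sizes 4 and 6 protect better than 2, 4 and 6 (0.633 against 0.756 in step 4), because the second set still contains pairs; either improves on 1.00. The cost is a new pharmacy list and a possible imbalance of up to 3 per stratum, against 1 with blocks of 2.

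**For patients already randomised.** Ask the pharmacy to list every patient whose allocation was released to investigators, with the date and the block partner. If there were none, one sentence in the report closes that route. If there were any, add a sensitivity run of the primary ANCOVA that drops the assessments of both patients after the unblinding date.

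The cost is one extra analysis with noisier AUCs for those patients: on the assumptions of step 6, error SD 0.94σ with 12 months kept and 1.41σ with 6, against 0.49σ with full follow-up. A patient left with no score after Month 0 has no treatment-phase AUC under SAP 4.2 and drops out of that run. This includes any partner randomised after the unblinding.
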